9 DATA HANDLING RULES AND DEFINITIONS

9.1 Data Handling Conventions

9.1.1 Study Days and Duration

Study Day 1 is the date of first dose of randomized treatment with study drug after randomization; it is typically the date of randomization.

Study days will be numbered relative to the first day of randomized study drug administration.

- Study days will be numbered relative to study start (i.e., ..., -2, -1, 1, 2, ...; with **Day 1** being the start of study drug and **Day -1** being the day before the start of study drug).
- The elapsed time since Day 1 for an event (e.g. onset of an adverse event) will be calculated as [date of event – date of Day 1 + 1].
- For the purpose of converting days to years or months, one year = 365.25 days, and one month = 30.44 days.

Study Duration is defined as follows:

$$\begin{aligned} & (\text{Date of Double Blind Treatment completion or discontinuation} \\ & \quad - \text{Date of First Day of Study Drug}) + 1 \end{aligned}$$

9.1.2 Visit Windows for Repeated Measures Efficacy Analyses

All efficacy measures that are repeated (repeated measures) over the duration of the study and analyzed with statistical models for repeated measures (i.e., linear and logistic MMRM models) will have efficacy windows defined for these analyses.

For efficacy measures that occur only once post-baseline during the study at Week 24/ET, the nominal study visit (Week 24/ET) will be used for the efficacy analyses.

All safety analyses will be based upon nominal visit days.

9.1.2.1 Efficacy Windows for 7-Day Average Daily Nasal Symptom Diaries and CSNS

As discussed in Section 9.3.1 below, electronic diaries will be used by subjects during the single-blind placebo run-in period and during the first 12-weeks of the 24-week double-blind treatment period in this study to capture daily nasal symptoms and the CSNS. Table 9.1 displays the efficacy windows defined for the 7-day average Daily Nasal Symptoms diary and CSNS for each study week from baseline (Visit 2) through Week 12 (Visit 5). Scheduled study visits corresponding to study endpoints are included and highlighted in the table for reference.

The efficacy windows defined in Table 9.1 may yield intermittent missing data due to a missing 7-day average from the daily nasal symptom diary, as described in Section 9.3.1. Missing data will be estimated within the MMRM models under the assumption they are Missing at Random (MAR), conditional on the observed values and the statistical model (Mallinckrodt, Lane, Schnell, Peng, & Mancuso, 2008).

Table 9.1: Windows for 7-Day Average Individual Daily Nasal Symptom Diary and CSNS

Study Visit	Study Week	Nominal Visit Day	Interval (Days)
2	Baseline	1	[-7, -1]
	1	7	[2, 6]
	2	14	[7, 13]
	3	21	[14, 20]
3	4	28	[21, 27]
	5	35	[28, 34]
	6	42	[35, 41]
	7	49	[42, 48]
4	8	56	[49, 55]
	9	63	[56, 62]
	10	70	[63, 69]
	11	77	[70, 76]
5	12	84	[77, 83]

9.1.2.2 Efficacy Windows for Repeated Measures based on Clinic Visits

Several secondary efficacy endpoints in this study are based on efficacy measures that are repeated over several clinical visits; these include the SNOT-22 Total and Domain Scores, PSQI Global and Component Scores, PGIC, and HPQ. Since these endpoints include repeated measures, they are analyzed using MMRM models.

Table 9.2 displays the windows for the efficacy measures at each scheduled clinic visit. If multiple observations for a subject occur within the same visit window, the observation closest to the nominal visit day will be used; in the case of two equidistant observations the later one will be used. The efficacy windows defined in Table 9.2 may yield intermittent missing data due to a missed clinic visit. Missing data will be estimated within the MMRM models under the assumption they are MAR, conditional on the observed values and the statistical model (Mallinckrodt, Lane, Schnell, Peng, & Mancuso, 2008).

Subjects who discontinue from double-blind study prematurely are instructed to fill out the assessments in the Week 24/ET visit form. For efficacy endpoints described above, these data will be windowed as defined in Table 9.2 and used at the defined visit. For example, if a subject has an ET visit on Day 50 the value will be used as the Week 8 visit value, and the subsequent visits Week 12 and Week 24/ET will be missing. If a subject has an ET visit on Day 120, the value will be used as the Week 24/ET visit value and there is no monotone missing data for this subject.

Table 9.2: Windows for Repeated Measures based on Clinic Visits

Visit Number	Nominal Visit Day	Interval (Days)
2: Baseline	1	[-21 , 1]
3: Week 4	28	[2, 42]
4: Week 8	56	[43, 70]
5: Week 12	84	[71, 98]
6: Week 24/ET	168	[\geq 99]

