7.5.5 PSQI Global and Component Scores

The Pittsburgh Sleep Quality Index (PSQI) is a validated, self-rated questionnaire, which assesses sleep quality and disturbances over a 1-month time interval; further details on the PSQI instrument are provided in Section 9.3.7. PSQI is measured at baseline, Week 12, and Week 24/ET. For PSQI Global score, a poor score is defined as follows: for a subject with a baseline PSQI Global score ≥ 17 , a value of ‘21’ is assigned; if baseline PSQI Global score < 17 , a poor score is defined as baseline PSQI Global score + 4 for the composite strategy, per the primary estimand. For PSQI component scores, the worst score for the component will be assigned.

Changes from baseline to Week 12 and Week 24/ET in PSQI Global score and component scores (reference Appendix, Section 13.1) will be analyzed using the MMRM model described in Section 7.1.5, where the repeated measures include change from baseline scores at Week 12 and 24/ET. The model-based LS mean difference between each active treatment group and placebo (active-placebo), 95% CI, and nominal p-value will be displayed for each analysis time point.

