7.5.8 PGIC - “Subject” Global Impression of Change

PGIC and endpoints “Improved” and “Much Improved” are defined in Section 9.3.8. PGIC is measured at Weeks 4 and 24/ET. For PGIC endpoints, the worst score of “Not Improved” will be assigned for each endpoint (Table 9.6) for the composite strategy, per the primary estimand.

The proportion of subjects “Improved” or “Much Improved” will be compared between treatments (each active versus placebo) based on a logistic regression MMRM using the generalized linear mixed model (GLMM). The logistic regression MMRM model will include categorical effects for previous sinus surgery (Y,N), nasal polyp status (present, absent), treatment (OPN-375 186 µg, OPN-375 372 µg, placebo), week (4, 24/ET) and treatment-by-week interaction,. Treatment group comparisons will be estimated from the least squares mean difference between treatments from treatment-by-visit interaction and will be presented as odds ratios with accompanying p-

values and 95% confidence intervals. The model-based LS Mean estimate of the percentage response in each treatment group will also be presented.

Model parameters will be estimated using restricted pseudo-likelihood with Newton-Raphson ridging optimization and the Kenward-Roger method for calculating the denominator degrees of freedom. An unstructured covariance matrix will be used to estimate within-subject error. The logistic regression MMRM will be implemented in SAS PROC GLIMMIX.

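### SAP Table 9.2 assigns early-termination PSQI (Days 2–70) and PGIC (Days 43–98) values to visits that their models do not contain, and SAP 9.1.5 contradicts that rule

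*SAP*

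**What the plan says.** SAP 9.1.2.2 lists the clinic-visit instruments it covers: "these include the SNOT-22 Total and Domain Scores, PSQI Global and Component Scores, PGIC, and HPQ". On subjects who leave early it states: "For efficacy endpoints described above, these data will be windowed as defined in Table 9.2 and used at the defined visit". Table 9.2 has four post-baseline windows: Week 4 is Days 2–42, Week 8 is Days 43–70, Week 12 is Days 71–98, and Week 24/ET is Day 99 onward.

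Two examples follow. In the first, "if a subject has an ET visit on Day 50 the value will be used as the Week 8 visit value". Nothing is then carried forward: both remaining time points, Weeks 12 and 24/ET, are left empty for that subject. In the second, "If a subject has an ET visit on Day 120, the value will be used as the Week 24/ET visit value".

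The models use fewer visits than the table:

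- **PSQI (SAP 7.5.5).** "PSQI is measured at baseline, Week 12, and Week 24/ET", and the model is one "where the repeated measures include change from baseline scores at Week 12 and 24/ET". The pooled PSQI analysis in SAP 7.5.5.1 uses the same model with a protocol term added.
- **PGIC (SAP 7.5.8).** The logistic repeated-measures model has "week (4, 24/ET) and treatment-by-week interaction".
- **SNOT-22 (SAP 7.5.2).** All four visits are modelled.

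Two other rules bear on the same data. SAP 9.1.5 defines the Week 24/ET value as each subject's final available post-baseline measurement, including when the subject stops before Week 24. SAP Table 9.6 (and Protocol Table 3) counts a missing PGIC as not improved, whereas SAP 9.1.2.2 treats missing values as missing at random (MAR).

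**The concern.** Table 9.2 fits an instrument collected at every clinic visit. Applied to an instrument collected at fewer visits, it gives some ET values a visit label that the instrument's model does not include. The Day 50 example rules out moving such a value to a later visit, because it declares those visits missing.

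For PSQI, a subject who leaves by Day 70 has normally had no scheduled post-baseline PSQI. The ET questionnaire is then the only one, and the model cannot use it. The MAR argument in 9.1.2.2 conditions on observed values, but this observed value is outside the model.

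For PGIC, the subject has normally already given a Week 4 rating and stays in the model, but the later ET rating goes unused. What stands at Week 24/ET depends on which rule is followed: MAR under 9.1.2.2, or not improved under Table 9.6. Under the second, a subject who reported improvement at the ET visit could be analysed as not improved.

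At stake are two patient-reported secondary endpoints, including the pooled PSQI global score, and whether two programmers working from this SAP would build the same dataset.

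**Working it through.** **Inputs.** Windows from SAP Table 9.2; model visits from SAP 7.5.2, 7.5.5 and 7.5.8; visit tolerance of ±7 days from the Schedule of Study Procedures; 333 subjects from SAP 4.2; 168 days as the nominal Week 24. The documents give neither a discontinuation rate nor its timing. I assume 8–16%, spread evenly.

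**Step 1: reproduce the SAP's examples.** Day 50 lies in 43–70, hence Week 8. Day 120 is at or above 99, hence Week 24/ET. Both match.

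**Step 2: compare each window with each model.**

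| Window | Days | SNOT-22 | PSQI | PGIC |
|---|---|---|---|---|
| Week 4 | 2–42 | in model | not in model | in model |
| Week 8 | 43–70 | in model | not in model | not in model |
| Week 12 | 71–98 | in model | in model | not in model |
| Week 24/ET | 99 on | in model | in model | in model |

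Days with no place in the model:
- PSQI: Days 2–70, 70 − 2 + 1 = 69 days.
- PGIC: Days 43–98, 98 − 43 + 1 = 56 days.
- SNOT-22: none.

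**Step 3: are scheduled visits affected?** With ±7 days, Week 4 falls on Days 21–35, Week 8 on 49–63, Week 12 on 77–91 and Week 24 on 161–175. Each lies inside its own window. Only ET and other off-schedule values are affected.

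**Step 4: upper bound on size.** Share of ET values affected under even timing:
- PSQI: 69/168 = 41%.
- PGIC: 56/168 = 33%.

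Subjects discontinuing: 0.08 × 333 = 26.6 to 0.16 × 333 = 53.3.
- PSQI: 26.6 × 0.41 ≈ 11 to 53.3 × 0.41 ≈ 22.
- PGIC: 26.6 × 0.33 ≈ 9 to 53.3 × 0.33 ≈ 18.

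If ET visits are instead spread over Days 2–160 (159 days, ending before the Week 24 visit window opens), the shares are 69/159 = 43% and 56/159 = 35%.

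**Step 5: what lowers these counts.**
- Not every subject who leaves attends an ET visit.
- Subjects with systemic corticosteroids for CRS or nasal surgery receive assigned scores (SAP 7.1.3, 7.5.5, 7.5.8), so their ET value is not used in any case.
- The Full Analysis Set needs a Week 2 or Week 4 CSNS average, and the Week 2 window opens on Day 7 (SAP 5.5, Table 9.1). An ET visit on Days 2–6 is therefore outside the efficacy population. This alone takes the PSQI range to 64 days, or 64/168 = 38%.

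**Step 6: would a wider Week 4 window rescue PGIC?** Suppose Week 4 covered Days 2–98. When a window holds several values, SAP 9.1.2.2 keeps the one nearest the nominal day. The scheduled rating is at most 7 days from Day 28; an ET rating on Day 43 or later is at least 43 − 28 = 15 days away. The scheduled rating always wins and the ET rating stays unused. Widening Week 4 does not help.

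**The case against.** The strongest reply is SAP 9.1.5. It is not limited to particular endpoints, and read literally it keeps every ET PSQI and PGIC as the Week 24/ET value. A reader might infer that the SAP instructs the analyst to discard these values; no sentence says so. The loss follows from a visit label outside the model together with later visits being declared missing. This stands as a qualification, but it does not remove the problem. Section 9.1.2.2 is the more specific rule, names both instruments and gives a worked example that 9.1.5 contradicts. One of the two has to change.

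A reader might also infer that PGIC subjects drop out as PSQI subjects do. The documents do not support that: a subject reaching Day 43 has normally given the Week 4 rating and remains in the model.

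A third tempting inference is that the unused values come mainly from subjects leaving for lack of effect. Protocol 4.3 lists lack of efficacy as a reason to stop study treatment, and strongly encourages those subjects to stay in the study for all procedures; it is not among the listed reasons for leaving the study. No direction of bias can be claimed.

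Finally, an early PSQI is not an ideal Week 12 measurement, since the instrument has a 1-month recall. That is a fair cost of the remedy, but not a reason to leave the rule unstated.

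**Conclusion.** The point holds. Under SAP 9.1.2.2 an ET PSQI on Days 2–70 and an ET PGIC on Days 43–98 are assigned to visits outside their models. For PSQI, a subject with no other post-baseline value contributes nothing to either the study-level or the pooled analysis. For PGIC, an observed rating goes unused, and the Week 24/ET status is left to two conflicting rules. Section 9.1.5 contradicts 9.1.2.2 for both instruments.

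The day ranges follow exactly from the SAP. The counts do not: about 11–22 (PSQI) and 9–18 (PGIC) of 333 subjects are upper bounds. They rest on an assumed 8–16% discontinuation rate, even timing over 168 days, and every such subject completing an ET questionnaire.

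It would be wrong to read this as a threat to the trial's main conclusions. PSQI and PGIC are other secondary endpoints with nominal p-values (SAP 7), and the co-primary and key secondary analyses do not use Table 9.2. The correction is still worth making, because it needs only a little SAP text and keeps data that the schedule collects.

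**What to change.** Before unblinding, amend SAP 9.1.2.2 as follows:

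1. **PSQI:** windows built from its own visits, with post-baseline through Day 98 assigned to Week 12 and Day 99 onward to Week 24/ET. The 69 days without a model visit fall to none. Apply the same windows in the pooled analysis.
2. **PGIC:** assign an ET rating obtained after the Week 4 window (Day 43 onward) to Week 24/ET. Do not widen the Week 4 window, for the reason in Step 6.
3. **SNOT-22 and HPQ:** keep Table 9.2. Both are collected at all four visits, and HPQ variables are in any case defined outside this SAP.
4. **Reconcile the rules:** state whether 9.1.2.2 or 9.1.5 governs repeated-measures endpoints, and whether a missing PGIC is handled as MAR or coded not improved as in Table 9.6.

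The cost is a few lines of SAP text and some programming, with no new data collection. The downside is that some early ET values will count at a later nominal visit, and an early PSQI may reflect partly pre-treatment sleep because of its 1-month recall. A table of ET values by actual study day and assigned visit would let readers judge how much this matters.

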9.1.3 Baseline Value

Baseline is defined as the last measurement prior to receiving the first dose of double-blind treatment. For nasoendoscopy nasal examination, the assessment at Screening (Visit 1) will be used as the baseline assessment; for CT scan, the date of the procedure during the placebo run-in period will be considered the baseline visit. For all other procedures, the assessment at Visit 2 (Day 1) is considered the baseline assessment.

For the individual daily nasal symptom scores and CSNS, the 7-day average of the last 7 days in the run-in period immediately prior to randomization is considered the baseline value. Reference Section 9.3.1 and Table 9.1 above for further details.

9.1.4 Enrollment Date

The enrollment date is the date the subject signed informed consent to be enrolled into the study. i.e., screening visit date (Visit 1).

9.1.5 Week 24/End of Treatment (ET)

Week 24/ET value is the last non-missing post-baseline value for each subject. This value will occur either at Week 24 or earlier if, for example, the subject discontinues the study prior to Week 24.

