4.6 Considerations for statistical analysis resulting from the COVID-19 PHE

4.6.1 Co-Primary Endpoints

Since the co-primary efficacy variable CSNS is based on electronic diaries used by subjects during this study, as described in Section 9.3.1, there is no anticipated impact of COVID-19 on the subject's ability to complete the diaries per the protocol. Therefore, there is no anticipated impact of COVID-19 on this co-primary endpoint.

For the co-primary endpoint APOV, the endpoint CT scan will occur at the Week 24 visit, or the ET visit if the subjects discontinues the study prior to Week 24. Since subjects must visit the clinic for the CT scan, subjects may be impacted by COVID-19 in a manner similar to other acute illnesses as described in the Protocol, Amendment 6, Section 6. In this circumstance a subject must be symptom-free for at least 28 days prior to undergoing the Week 24/ET CT scan, and consequently the Week 24/ET visit may be delayed. Subjects are instructed to continue on treatment until the EOS CT scan can be completed. There is no anticipated impact of such a delay on the APOV co-primary endpoint.

Thus, there is no practical impact of the COVID-19 PHE on either of the co-primary endpoints.

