7.1.3 Primary Estimand

The primary efficacy estimand is the difference between each active treatment of twice-daily doses of 186 μg and 372 μg of OPN-375 and placebo for each of the co-primary endpoints.

For the primary estimand, intercurrent events will be addressed as follows:

1. Systemic corticosteroids use for CRS exacerbation or worsening of CRS nasal/sinus symptoms: a composite strategy will be employed with a poor score assigned to this event.

For CSNS, a value of '9' will be assigned; further detail regarding the assignment of a worst score to the diary data are provided in Section 9.3.1. For APOV, a poor score is defined as follows: for a subject with a baseline APOV $\geq 75\%$, a value of '100%' is assigned; if baseline APOV $< 75\%$, a poor score is defined as baseline APOV + 25%.

The rationale for assignment of a poor score is provided in Section [7.1.4](#) below. Further detail regarding the handling of a missing POV in individual sinuses is provided in Section [9.3.2](#).

Systemic corticosteroid use for other indications will be considered a treatment and study discontinuation event (reference criteria 3c).

2. Nasal surgery: composite strategy with poor scores assigned as above.
3. Treatment Discontinuation: treatment policy strategy; subjects may continue in the study until one of the following three mutually exclusive outcomes:
 - a) Subject completes Week 24/ET CT scan. In the absence of an intercurrent event (systemic corticosteroids, nasal surgery) use the endpoint value;
 - b) An intercurrent event (systemic corticosteroids for CRS exacerbation or worsening of CRS nasal/sinus symptoms, nasal surgery) occurs: use composite strategy and assign poor score as described above (reference criteria 1, 2);
 - c) Subject discontinues the study. Missing data due to study discontinuation following treatment discontinuation will be imputed; further detail on the imputation method is provided in Section [7.1.5](#) for each of the co-primary endpoints.

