For the treatment policy estimand, (reference Section 7.1.3, criteria 3, c), missing data due to study discontinuation will be imputed with a pattern mixture model (PMM) multiple imputation (MI) using the Jump-to-Control (J2C) method. The PMM assumes that the missing data at Week 24/ET on the control arm (placebo) is MAR, and the missing data on the active treatment arms have the profile of the control arm at Week 24/ET.

Multiple imputation using a PMM with J2C method will be conducted using the sequential modeling method as described in (O'Kelly & Ratitch, 2014). Further detail on the MI implementation, and statistical analysis and inference is provided in Section 10.

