10.2 Multiple Imputation Method – PMM with J2C

As described in Section [7.1.3](#) for the treatment policy estimand, missing data due to study discontinuation will be imputed with a multiple imputation method (MI) for the following efficacy

variables: APOV, WPOV-E, WPOV-M, WPOV; LM, ZLM, and WZLM scores; SF36-v2 scores, QIDS total score, SIT score, and EQ-5D-5L VAS.

Multiple imputation with a PMM and J2C method will be conducted using the sequential modeling method as described in (O'Kelly & Ratitch, 2014), Chapter 7. To implement J2C method, first the initial dataset is used to impute missing data in the control group with multiple imputation under MAR assumption. The initial dataset used is the analysis dataset – in this case a dataset with a single post-baseline observation at Week 24/ET; this dataset is referred to as *EFF*. Therefore, MI is performed on a single post-baseline observation with missing data.

The statistical model used to estimate parameters in the imputation of missing data for analysis variable in the control group under MAR assumption includes the following terms: treatment, baseline covariate, nasal polyp status (present, absent), previous sinus surgery (Y, N). This model is implemented in PROC MI with MONOTONE REGRESSION statement. The output dataset is referred to as *EFF_MI_MAR*. This dataset, after some data manipulation to restore the missing data in the active active treatment arms, is the input dataset for implementation of J2C method in SAS, which involves three steps for imputing a single time point.

Step 1: Remove subjects in the active treatment groups with complete data at Week 24/ET (OUTPUT REST_V6). Keep remaining subjects (OUTPUT IMPUTE_V6):

- a) Subjects in active treatment groups with data to be imputed at Week 24/ET
- b) Control subjects with observed and multiply imputed data under MAR at Week 24/ET

Step 2: Multiple imputation of Week 24/ET missing data (INPUT IMPUTE_V6) using a regression of Week 24/ET analysis variable on baseline value of endpoint only (OUTPUT IMPUTED_V6).

Since the regression method uses only observed data to estimate regression parameters for the MI, only control subjects are used for the imputation of missing values at Week 24/ET in the active treatment groups.

Step 3: Reassemble (concatenate) datasets (REST_V6, IMPUTED_V6).

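### Does using an early-termination CT scan as the Week 24 APOV value, with no analysis that isolates this choice, call for a change to the SAP?

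*SAP*

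**What the plan says.** Three places in the SAP fix the APOV value of a study dropout who has an ET scan. Section 9.1.5 says that the "Week 24/ET value is the last non-missing post-baseline value for each subject". Section 9.1.2 adds: "For efficacy measures that occur only once post-baseline during the study at Week 24/ET, the nominal study visit (Week 24/ET) will be used". Section 4.6.1 places the endpoint scan at Week 24, "or the ET visit if the subjects discontinues the study prior to Week 24". None sets a minimum day. Protocol 6.5 asks early withdrawers to return for a visit that includes a CT scan.

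The primary estimand (SAP 7.1.3) takes such a scan as observed under branch 3a: "Subject completes Week 24/ET CT scan. In the absence of an intercurrent event (systemic corticosteroids, nasal surgery) use the endpoint value". Branch 3c covers missing data after the subject leaves the study. For APOV, SAP 7.1.5 specifies that "missing data due to study discontinuation will be imputed with a pattern mixture model (PMM) multiple imputation (MI) using the Jump-to-Control (J2C) method". SAP 10.2 builds the imputation on one slot per subject, "in this case a dataset with a single post-baseline observation at Week 24/ET".

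The repeated questionnaires (SNOT-22, PSQI, PGIC, HPQ) follow SAP 9.1.2.2 and Table 9.2. There an ET visit on Day 50 counts as Week 8 and leaves Week 24/ET missing; only Day 99 onward counts as Week 24/ET.

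**The concern.** A scan taken a few weeks after randomization can stand in for the 24-week value of a co-primary endpoint, while the same SAP declines to treat a Day 50 questionnaire that way. Because the ET scan fills the only slot, J2C reaches mainly dropouts with no scan. Placebo ET scans also enter the regression that supplies the imputed values, since Step 1 of SAP 10.2 keeps "Control subjects with observed and multiply imputed data under MAR at Week 24/ET". The tipping-point analysis shifts imputed values only, and the observed-cases analysis keeps the scan, so neither tests the choice.

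Two wording points add to the impression of a gap. SAP 9.1.5 is not limited to endpoints measured once after baseline. And a subject who takes systemic steroids for another indication is sent to a branch about missing data even if a scan exists: "Systemic corticosteroid use for other indications will be considered a treatment and study discontinuation event (reference criteria 3c". Protocol 9.3.3 points only to criterion 3. If these choices moved the APOV estimate materially, a co-primary conclusion would be at stake.

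**Working it through.** **1. The plan's own figure.** SAP 4.2 gives a difference of 11.3, SD 27, 111 per group, two-sided 5% and 88% power. SE = 27 × √(2/111) = 3.624. 11.3/3.624 = 3.118, and Φ(3.118 − 1.960) = 87.7% (87.4% with the noncentral t). The stated power reproduces.

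**2. The rules by ET day.**

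| ET day | Questionnaires (Table 9.2) | APOV (4.6.1, 9.1.2, 9.1.5) |
|---|---|---|
| 20 | Week 4; Week 24/ET missing | Week 24/ET |
| 50 | Week 8; Week 24/ET missing | Week 24/ET |
| 90, 98 | Week 12; Week 24/ET missing | Week 24/ET |
| 99, 120 | Week 24/ET | Week 24/ET |

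The columns concern different endpoints, so they do not contradict each other. A clash arises only if 9.1.5 is applied literally to the questionnaires. Section 9.1.2.2 assigns their ET data to the Table 9.2 windows and works two examples, so the specific rule governs. The SNOT-22 and PSQI analyses carry nominal p-values only (SAP 7.5.2, 7.5.5).

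**3. How early is early.** The full analysis set needs a Week 2 or Week 4 CSNS average (SAP 5.5), and the Week 2 window opens on Day 7 (Table 9.1). Dropouts with no diary data from Day 7 onward are not analysed.

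**4. What the planned APOV analyses do to a dropout's ET scan.**
- Supplementary estimand (7.2.1): treatment discontinuation receives a poor score, namely baseline + 25, or 100% if baseline is 75% or more. Steroid handling changes too.
- Ranked ANCOVA (7.2.2): can be read as substituting baseline; it also changes the composite score and the scale.
- Observed cases (7.2.3): scan kept.
- Tipping point (7.2.4): scan untouched.
- Per-protocol set (5.6): early scans are not among the listed examples.

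So the scans are stressed, but no analysis varies this rule alone.

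**5. Steroids for another indication.** Branch 3a requires the absence of systemic corticosteroids, with no CRS limit. Branch 3b is limited to CRS steroids or surgery. By elimination the subject falls in 3c, which the SAP names. The protocol's criterion 3 contains 3c, so the SAP is narrower, not contradictory.

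**6. Size.** The documents give no dropout, ET-scan or time-course data. Assumed inputs:
- D = 11.3 (the planning effect)
- d = share leaving without a steroid or surgery event, 5–15%
- q = share of those scanned, 50–80%
- f = share of D present at the scan, 0–1
- e = share of dropouts before Day 99 = 98/168 = 0.583 (uniform dropout)

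Formulas:
- Plan: D(1−d) + D·d·q·f
- Dropout scans before Day 99 set to missing: D(1−d) + D·d·(1−e)·q·f
- All dropout ET scans set to missing: D(1−d)

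Central case (d = 0.10, q = 0.65, f = 0.5):
- Plan: 10.17 + 0.367 = 10.54
- Day 99 version: 10.17 + 0.153 = 10.32; shift 0.21 points = 0.06 SE
- All-dropout version: 10.17; shift 0.37 points = 0.10 SE
- Power: 82.5%, 80.9% and 79.8%

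Upper corner (d = 0.15, q = 0.8, f = 1):
- All-dropout shift: 11.3 × 0.15 × 0.8 = 1.36 points (0.37 SE)
- Day 99 shift: 1.356 × 0.583 = 0.79 points (0.22 SE)

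The Day 99 version would set 111·d·q·e = 1.6 to 7.8 scans per arm to missing.

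Two refinements reduce these shifts. Starting dropout at Day 7 gives e = 92/162 = 0.568 and a maximum Day 99 shift of 0.77. If the effect grows linearly to Day 168, scans before Day 99 average f = 49/168 = 0.29, and the central shift is 11.3 × 0.10 × 0.65 × 0.583 × 0.29 = 0.12 points (0.03 SE).

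**7. Under no effect.** With equal dropout and scan rates across arms the shift is zero. With 5% active and 15% placebo dropout, q = 0.65, and an assumed 5-point placebo improvement wholly absent at the ET scan:
- Placebo mean used for imputation: −5 × 0.85/(0.85 + 0.0975) = −4.486
- Shift: −5 × 0.95 + 4.486 × 0.9825 = −0.34 points (0.09 SE)
- Two-sided error: about 5.1%

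**The case for a change.** The best case for a change runs as follows. APOV is co-primary. The SAP itself refuses to read a questionnaire before Day 99 as Week 24/ET. Protocol 1.2 reports that improvements in the earlier polyp studies generally kept growing through Week 24, so scan timing could matter. The analyses that displace ET scans alter other features as well, so a reader cannot learn what the carry-forward alone contributes. SAP Section 10 promises enough detail for independent replication, and an existing scan after steroids for another indication is not explicitly set aside. The remedy would be cheap: a limiting sentence, one extra run of the Section 10.2 method, and a table of scan days.

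Some of this stands. No planned analysis isolates the rule, 9.1.5 is worded too broadly, and 7.1.3 could say outright what happens to that scan. But the polyp-study evidence is indirect, coming from an open-label phase and other endpoints. J2C is itself an assumption, so a departure from it shows sensitivity, not bias. It would be wrong to say the scans go unchecked, because the supplementary estimand replaces them with a value that is always worse than baseline or at the ceiling. Reporting also exists in part: discontinuations and reasons by arm (SAP 6.1), a subject listing of intercurrent events with outcomes under both estimands (6.1.1), and exposure duration by arm (8.1), although none gives the scan day.

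**Conclusion.** No change is needed. Using the ET scan is a deliberate, prespecified choice that keeps observed data, and it agrees with the endpoint's name throughout both documents. Protocol 4.3 strongly encourages subjects who stop treatment to stay in the study, which limits the number of early scans. The breadth of 9.1.5 is a drafting slip that 9.1.2.2 and Table 9.2 already resolve, and the steroid branch is settled by elimination and by the SAP's own pointer to 3c.

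What is left is one possible extra sensitivity analysis whose cut-off day the documents do not dictate. Its central shift is 0.06 SE or less for a Day 99 cut-off, and at most 0.22 SE over the ranges tried. Those sizes depend wholly on assumed dropout, scan and retention rates; neither size nor direction can be established from the documents. No inflation of the Type I error is shown. The analysis team may add a clarifying sentence or a table of scan days, but neither would alter what the trial does or concludes.
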